3.7 Benefit/Risk Considerations

Potential Risks

RSLV-132 has been studied in 24 healthy volunteers and 24 patients with SLE. The most frequently reported adverse events were headache, nausea, and upper respiratory tract infection, each of which occurred in 5 subjects. Infection of hair follicles was also reported in one subject. Reactions at the site of the injection, such as redness, bleeding and bruising, were reported in several subjects.

In addition to the risks listed above, there may be some unknown or infrequent and unforeseeable risks, including that of unknown drug interactions associated with the use of RSLV-132. The administration of protein drugs like RSLV-132 may result in serious and potentially life-threatening anaphylactic reactions. While none of these reactions have occurred in the previous studies with RSLV-132, it is possible they could occur in the future. Genotoxicity, Carcinogenicity and Reproductive Toxicity studies have not been conducted for RSLV-132 and therefore the risks of these events, while considered low for the class of compound and mechanisms of action, are unknown.

Potential Benefits

Of the evaluable subjects in the 132-02 multi-dose SLE study, 7/16 (44%) had an improvement in SLEDAI score, however given the small size of the study the data are not statistically significant. No studies in pSS have been conducted to date, therefore no data are available to evaluate potential benefits.

Risk minimization

The study population will be carefully chosen using the inclusion and exclusion criteria to minimize the potential for adverse events. Subjects will be informed in a timely manner of any new information about the study drug and allowed to decide if they wish to continue the study. Subjects will be advised to seek medical attention at the appearance of any potential side effects. All subjects will be followed up for 18 weeks following the last infusion of RSLV-132 to allow early detection and management of any delayed significant AE.

The medical monitor will continually review the safety data to identify any trends that may pose significant risk. In addition, processes are in place to communicate serious adverse events to the sponsor and for reporting SUSARs to the relevant regulatory agencies and the Eudra Vigilance Clinical Trial Module.

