1.11 Evaluations by Day

- Screening Procedures:
 - informed consent;
 - assess inclusion/exclusion criteria;
 - demographic data;
 - weight and height;
 - physical examination;
 - complete medical and medication history;
 - vital signs;
 - hepatitis B, C, and HIV antibody tests;
 - serum pregnancy test;
 - chem-21 (see Appendix B), CBC, and UA;
 - interferon-stimulated gene expression analysis (whole blood);
 - anti Ro-52/Ro-60 autoantibodies;
 - FSH (when required to confirm menopause in female subjects)

- Baseline Procedures:
 - confirmation of inclusion/exclusion criteria;
 - physical examination;
 - adverse event baseline assessment;
 - interim medical and medication history;
 - vital signs;
 - measurement of disease activity (ESSDAI, PGA, Schirmer's, stimulated and unstimulated salivary flow);
 - measurement of patient reported outcomes (ESSPRI, FACIT, Profile of fatigue, EQ-5D-L, Fatigue VAS, Neuropsychological analysis);
 - optional minor salivary gland biopsy;
 - urine pregnancy test;
 - chem-21 (see Appendix B), CBC, and UA;
 - serum for study drug concentration and RNase activity;
 - serum for serum protein analysis;
 - whole blood for ESR
 - whole blood for DNA analysis;
 - whole blood for measurement of RNA gene expression;
 - serum for anti Ro-52/Ro-60, total immunoglobulins, C3, and C4;
 - serum for anti-RSLV-132 antibodies;
 - study drug administration.

Additional Procedures:

The following procedures will be performed at various visits during the study. A total of 9 post-baseline visits will occur; once weekly for two weeks, then every two weeks for 14 weeks, plus one further visit 8 weeks after the last study drug administration. There will then be two additional telephone contacts made to subjects at weeks 13 and 18 after the last dose, to monitor any potential late-emerging adverse events. See section 13 and the schedule of events for the specific procedures and collection time points.

- physical exam;
- vital signs;
- adverse event assessment;
- medication history;
- measurement of disease activity (ESSDAI, PGA, Schirmer's test, stimulated and unstimulated salivary flow);
- optional minor salivary gland biopsy;
- measurement of patient reported outcomes (ESSPRI, FACIT, Profile of fatigue, EQ-5D-L, Fatigue VAS, Neuropsychological analysis);
- serum sample for study drug concentration and RNase activity;
- serum for protein analysis;
- whole blood for ESR
- whole blood for DNA analysis;
- whole blood for gene expression profile;

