5.3 Overall Study Design and Plan

This is a double-blind, placebo-controlled study of 28 subjects with primary Sjogren's syndrome. Potential subjects will be screened to assess their eligibility to enter the study within sixty days prior to study entry (i.e., prior to Baseline visit). Following Baseline evaluations on Day 1 subjects will receive their first intravenous infusion of RSLV-132. Subjects will return to the research unit for additional visits as described in Appendix A. The subjects will be randomized 3:1 (active:placebo) to receive 8 intravenous administrations of 10 mg/kg of study drug or placebo on days: 1, 8, 15, 29, 43, 57, 71, and 85.

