6.3 Subject Withdrawal Criteria

Subjects will be informed that they are free to withdraw from the study at any time and for any reason. A subject should be discontinued from study drug treatment for any of the following reasons: AE which is either intolerable or poses safety concerns, pregnancy or disease worsening. The Investigator may also remove a subject from investigational treatment if, in the Investigator's opinion, it is not in the best interests of the subject to continue. Notification of discontinuation of investigational treatment will be made immediately to the Sponsor. In case of premature discontinuation of investigational treatment, efforts will be made to perform all protocol specified procedures for remaining study visit time points or at a minimum perform early termination assessments specified in Appendix A.

If a subject wishes to withdraw from the study, the site staff should confirm whether the subject is agreeable to continue the assessments without the investigational treatment or if they wish no further involvement in the study. In the latter case no further study-related evaluations will be performed and no additional data will be collected.

The date and the reason for discontinuation of investigational treatment or withdrawal from the study will be recorded on the subject's case report form. Subjects that withdraw after receiving study drug will not be replaced.

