10.3 Adverse Event Reporting

All AEs, both serious and non-serious, will be recorded on the AE CRF at each visit from the time the subject receives the first dose of study medication until Day 211, the final telephone contact with the subject. Any untoward event occurring between screening and baseline and deemed directly related to a study procedure by the investigator will be recorded on the AE CRF.

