13.5 Procedures on Days 29, 57, 85, and 99/Early Termination

Prior to study drug administration (pre-dose procedures):

- directed physical examination;
- urine pregnancy test (except Day 99);
- interim medical/medication history;
- vital signs (temperature, respiratory rate, blood pressure and pulse);
- chem-20 (see Appendix B), CBC, and UA;
- adverse event assessment;
- measure disease activity (ESSDAI, PGA, Schirmer's, stimulated and unstimulated salivary flow);
- patient reported outcomes (ESSPRI, FACIT, Profile of fatigue, EQ-5D-L, Fatigue VAS, Neuropsychological analysis (Day 99 only);
- optional minor salivary gland biopsy (consented subjects) (Day 99 only);
- serum for study drug concentration and RNase activity;
- serum protein analysis;
- whole blood for gene expression profile
- whole blood for ESR;
- serum for anti-Ro-52/Ro-60 autoantibodies
- serum for total immunoglobulins, C3 and C4;
- serum for anti-RSLV-132 antibodies (Day 29 only);

After completion of above assessments:

- o study drug administration (except Day 99)

13.6 Procedures on Day 141

The following procedures will be performed on Day 141:

- directed physical examination;
- pregnancy test (serum);
- interim medical/medication history;
- vital signs (temperature, respiratory rate, blood pressure and pulse);
- adverse event assessment;
- serum for study drug concentration and RNase activity;
- serum for assessment of anti-RSLV-132 antibodies;

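### The protocol promises every subject 18 weeks of safety follow-up after the last infusion, but section 6.3 accepts the Early Termination assessments as a minimum for those who stop study drug early

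*Protocol*

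**What the plan says.** Section 3.7 gives the follow-up as a safeguard against delayed adverse events: "All subjects will be followed up for 18 weeks following the last infusion of RSLV-132". The sentence covers all subjects and has no condition.

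Two other places match it. Section 1.11 says "There will then be two additional telephone contacts made to subjects at weeks 13 and 18 after the last dose". Section 10.3 records adverse events "until Day 211, the final telephone contact with the subject". The last planned infusion is on Day 85; section 5.3 lists study drug or "placebo on days: 1, 8, 15, 29, 43, 57, 71, and 85".

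Section 6.3 deals with subjects who stop treatment prematurely. It says "efforts will be made to perform all protocol specified procedures for remaining study visit time points or at a minimum perform early termination assessments", and refers to Appendix A for what those assessments are. In Appendix A they are the single Day 99/ET column. The reasons for stopping include safety: "A subject should be discontinued from study drug treatment for any of the following reasons: AE which is either intolerable or poses safety concerns". A subject who wants no further involvement at all gives no further data.

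Anti-drug antibody samples are listed at Baseline (section 13.3), at Day 29 only within the combined Day 29 to Day 99/ET list (section 13.5), and at Day 141 (section 13.6). Appendix A shows the same three days.

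**The concern.** A site that performs the ET assessments and nothing more has complied with section 6.3, yet the section 3.7 statement is then untrue for that subject. One section describes a safeguard to ethics committees and investigators; the other sets what sites must deliver, and sets it lower.

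The lower minimum covers, among others, subjects taken off drug for an adverse event. Delayed immune reactions are not a remote topic in this protocol. Section 3.5.3 reports a monkey sacrificed on Day 127 of dosing with changes attributed to a likely immunogenic or hypersensitivity reaction, and high-titre antibody responses in five of forty animals in the 26-week study. A subject who stops because of a suspected reaction and ends at ET would have neither a late safety contact nor a later antibody sample. In a study of 28 subjects whose safety data are summarised descriptively by group, unequal observation time between completers and early stoppers also makes the late adverse event tables harder to read.

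**Working it through.** **Inputs.** Promised follow-up: 18 weeks (section 3.7). Infusion days: 1, 8, 15, 29, 43, 57, 71, 85 (section 5.3). Later visits and calls: Days 99, 141, 176, 211 (Appendix A). Serum half-life: about 16 days, from the single-dose study in healthy volunteers (section 3.6.1).

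**Reproducing the plan's figure.** 18 × 7 = 126 days. Day 85 + 126 = Day 211. Likewise (141 − 85)/7 = 8 weeks, (176 − 85)/7 = 13 weeks and (211 − 85)/7 = 18 weeks. For a subject who receives all eight infusions, sections 1.11, 3.7 and 10.3 agree exactly.

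**Early stoppers.** Assume that ET takes place at the next scheduled visit. Follow-up at ET = next visit day − last infusion day; shortfall = 126 − that number.

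| Last infusion (day) | 18 weeks ends (day) | Next visit (day) | Follow-up at ET (days) | Shortfall (days) | Follow-up if everything to Day 211 is kept (days) |
|---|---|---|---|---|---|
| 1 | 127 | 8 | 7 | 119 | 210 |
| 8 | 134 | 15 | 7 | 119 | 203 |
| 15 | 141 | 29 | 14 | 112 | 196 |
| 29 | 155 | 43 | 14 | 112 | 182 |
| 43 | 169 | 57 | 14 | 112 | 168 |
| 57 | 183 | 71 | 14 | 112 | 154 |
| 71 | 197 | 85 | 14 | 112 | 140 |

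The section 6.3 minimum thus delivers 7/126 = 5.6% or 14/126 = 11.1% of the stated follow-up. The last column shows that section 6.3's first option, all remaining visits and calls, always gives at least 126 days. The conflict lies only in the fallback.

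**Drug still present.** With simple decay, the fraction remaining is 0.5^(days/16): 0.5^(7/16) = 0.74, 0.5^(14/16) = 0.55 and 0.5^(126/16) = 0.004. An ET-only subject would leave observation with more than half of the last dose still circulating, against under 1% at 18 weeks.

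**Does another section close the gap?**
- Section 10.3 sets a recording period to Day 211 but no contact for an ET-only subject at which a new event would be found.
- Section 10.4 covers serious events after the reporting period only where a causal link is suspected, and someone must first learn of them.
- Section 10.6 follows up events already judged related.
- Section 6.4 follows a positive pregnancy test to outcome.
- Section 13.7 describes the calls partly by reference to events ongoing at Day 141, a visit that an ET-only subject does not have.

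None of these requires an active contact after ET.

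**The case against.** The strongest reply is that section 6.3 does not tell sites to stop at ET. Its first request is for all remaining visits, and where a subject wishes to withdraw, staff must ask whether assessments can continue without treatment. Section 10.3 makes no exception for discontinued subjects, and section 1.11 counts the calls from the last dose without limiting them to completers. All of this stands. Ending at ET is permitted, not prescribed, and ET does not formally end safety reporting. What remains is that "or at a minimum perform early termination assessments specified in Appendix A" is an accepted endpoint for subjects who could still be reached, while section 3.7 admits no such endpoint. Loss of data after full withdrawal is unavoidable and is no part of this point.

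A reader might infer three stronger things that the protocol does not support.

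First, that ET has no pregnancy test. Section 13.5 lists "urine pregnancy test (except Day 99", but it names Day 99 and not ET. Section 6.3 points to Appendix A, whose row as read shows a urine test in the Day 99/ET column. That row may be displaced, because its serum test falls under a telephone contact. Absence is not established.

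Second, that early stoppers are the likeliest to have late events, so that the arm with more discontinuations looks too safe. Safety is one listed reason for stopping, but so are disease worsening, pregnancy and investigator judgement. No dropout rate is given, and no formal comparison of late events is specified.

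Third, that one subject's share of an arm measures the harm. It says nothing about events missed.

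**Conclusion.** The inconsistency is real and is in the current text. Section 3.7 states 18 weeks of follow-up for everyone, and section 6.3 accepts less for subjects who stop study drug early, including those who could still be contacted. The gap for such a subject is 112 or 119 of 126 days, assuming that ET falls at the next scheduled visit; a later ET would shrink it. The retained-drug fractions assume simple decay at the half-life of about 16 days. The antibody gap rests on the listed sampling days and would not apply where the ET visit coincides with Day 29 and that day's sample is taken.

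The number of affected subjects, the number of missed events and the direction of any bias cannot be derived from the protocol. This is a flaw in a stated safeguard and in data collection, so it belongs in the protocol and cannot be repaired in an analysis plan. It should be corrected, but it does not threaten the primary biomarker comparison.

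**What to change.** Reconcile sections 3.7, 6.3 and 10.3 for subjects who stop study drug but have not refused further contact. There are two ways to do it:

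- Bring the section 6.3 minimum into line with the 18-week statement, for example by tying the already planned telephone adverse event contacts to it.
- Limit the section 3.7 statement to subjects who complete the schedule, and describe the shorter minimum openly.

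Which to choose is for the sponsor and its clinical advisers; the point here is only that the sections must agree.

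Two clarifications belong in the same edit. State whether the Day 99 exceptions in section 13.5 (pregnancy test, antibody sample) apply when that visit serves as Early Termination, and check the Appendix A rows against that answer. Also state how the calls are timed for an early stopper. Section 1.11 counts them from the last dose, whereas section 13.1 counts scheduled calls from Baseline. For a last infusion on Day 29 that means Days 120 and 155 (29 + 91, 29 + 126) or Days 176 and 211.

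The cost is wording in sections 3.7, 6.3, 10.3 and 13.5 and, under the first option, a few calls for the few subjects concerned.

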3.8 Population

Subjects aged 18 to 85 years of age diagnosed with Primary Sjogren's Syndrome and meet the inclusion / exclusion criteria will be enrolled in the study.

4 STUDY OBJECTIVES AND PURPOSE

The present study will examine the role of circulating RNA complexed with autoantibodies and immune complexes and its role in activation of inflammatory pathways in patients with primary Sjogren's syndrome. The study will be conducted in a subset of Sjogren's patients who have elevated levels of SSA/Ro autoantibodies and a pattern of elevated interferon-stimulated gene expression in blood cells. Given the well-established inflammatory properties of RNA, RSLV-132 will be administered to digest the RNA which is circulating bound to autoantibodies and thereby attenuate chronic activation of multiple inflammatory pathways. A number of biochemical and clinical parameters will be analyzed to determine the potential therapeutic utility of nuclease therapy in Sjogren's syndrome.

5 STUDY DESIGN

5.1 Primary Study Endpoint

The primary endpoint of the study is to assess the following biochemical parameters in the active versus control groups comparing Baseline with Day 99:

- changes in blood cell gene expression or serum protein levels indicative of reduced inflammation.

5.2 Secondary Study Endpoints

The secondary endpoints of the study are to assess the following parameters in the active versus control groups comparing Baseline with Day 99:

- safety and tolerability;
- Ro52/60 autoantibody levels;
- total immunoglobulins;
- erythrocyte sedimentation rate (ESR);
- complement levels (C3 & C4)
- minor salivary gland histopathology
- minor salivary gland interferon-stimulated gene expression;
- disease activity (ESSDAI or PGA, Schirmer's test, stimulated and unstimulated salivary flow) (assessment worksheets provided in study regulatory binder);
- patient-reported outcomes as measured by the following: ESSPRI, FACIT, Profile of fatigue, EQ-5D-L, Fatigue VAS, and Neuropsychological analysis scales (assessment worksheets provided in study regulatory binder);
- Additional exploratory evaluations may be considered as driven by the evolving understanding of the mechanism of action, technical feasibility, and any other clinical or immunological information that may become available during the course of the clinical study. Note: Additional exploratory endpoints will be specified in a separate laboratory manual and will be reported separately to the main safety, tolerability and efficacy endpoints of the study.

5.3 Overall Study Design and Plan

This is a double-blind, placebo-controlled study of 28 subjects with primary Sjogren's syndrome. Potential subjects will be screened to assess their eligibility to enter the study within sixty days prior to study entry (i.e., prior to Baseline visit). Following Baseline evaluations on Day 1 subjects will receive their first intravenous infusion of RSLV-132. Subjects will return to the research unit for additional visits as described in Appendix A. The subjects will be randomized 3:1 (active:placebo) to receive 8 intravenous administrations of 10 mg/kg of study drug or placebo on days: 1, 8, 15, 29, 43, 57, 71, and 85.

5.4 Number of Subjects and Centers

Up to 28 subjects will be enrolled at approximately 2-3 clinical centers in the UK.

5.5 Estimated Study Duration

The duration of the study from Baseline to the End of Study visit is approximately 30 weeks.

5.6 Investigational Product Accountability

The unblinded pharmacist will maintain an accurate record of the receipt of the Investigational Product as shipped by the Sponsor (or designee), including the date received. In addition, an accurate drug disposition record will be kept, specifying the amount dispensed to each subject and the date of dispensation. The product accountability will be periodically monitored by an unblinded pharmacy monitor.

6 SELECTION AND WITHDRAWAL OF SUBJECTS

Subjects who meet all of the inclusion criteria at Screening, and none of the exclusion criteria will be eligible to be enrolled into the study.

6.1 Subject Inclusion Criteria

Subjects who meet all of the following criteria may be included in the study:

1. Meet 4 of the 6 criteria (must include histopathology or autoantibodies) of the 2002 American-European Consensus Group (AECG) criteria for Primary Sjogren's Syndrome.
2. elevated levels of anti Ro-52 or anti Ro-60 antibodies (within laboratory positive range);
3. positive interferon signature (whole blood cell interferon signature metric > -1);
4. stable medications used to treat Sjogren's syndrome for the 30 days prior to the Baseline visit;
5. able to communicate and able to provide valid, written informed consent;
6. ages 18 to 85 inclusive;
7. minimum weight of 45 kg;
8. Female participants shall be either of non-child-bearing potential (permanently sterilized by bilateral tubal occlusion, hysterectomy, or bilateral salpingectomy), or menopausal (more than one year since last menstrual cycle and confirmed by blood FSH levels \geq 22 mIU/mL) OR practicing highly effective contraception (e.g., oral, but not including progestogen-only oral contraceptives), injectable, implantable or transdermal contraceptives, a non-hormonal intrauterine device [IUD], or an intrauterine hormone releasing system [IUS]) for at least 2 months prior to dosing and until 125 days after the last dose. In terms of sexual relations, female participants not practicing highly effective contraception as described above should abstain or engage with male partners who are sterile or vasectomized. Female participants of child-bearing potential will also be required to have a negative serum pregnancy test [β -hCG] at Screening and negative pregnancy urine test at Baseline. Female participants must agree not to donate eggs from the first dose until 125 days after the last dose.
9. Male participants, who are not sterile or vasectomized, must agree to abstain or only engage with female partners who use highly effective contraception from the first dose until 125 days after the last dose. Male participants must also agree not to donate sperm from the first dose until 125 days after the last dose.

6.2 Subject Exclusion Criteria

Any of the following will exclude potential subjects from the study:

1. Previously diagnosed with systemic lupus, systemic sclerosis, or inflammatory myopathy.
2. Use of hydroxychloroquine within 30 days of Baseline;
3. use of cyclophosphamide within 180 days of Baseline;

4. use of belimumab, abatacept, or TNF inhibitors within 90 days of Baseline;
5. use of rituximab within 6 months of Baseline (documentation of B-cell counts within the normal range for the reference laboratory is required for subjects within 1 year of rituximab usage).
6. use of oral corticosteroids equivalent to prednisone dose of >10 mg/day within 30 days of Baseline;
7. past head and neck radiation;
8. current untreated lymphoma at Baseline;
9. known IgG4-related disease
10. graft versus host disease
11. the presence of a clinically significant infection in the judgement of the Investigator within seven days prior to the receipt of the first dose of study drug;
12. positive test for hepatitis B, C, or HIV at Screening;
13. participation in another clinical study with receipt of an investigational product within 3 months or 5 half- lives, of last administration (whichever is longer) from Baseline;
14. positive pregnancy test at Screening or Baseline;
15. female subjects currently pregnant or breast feeding at Baseline;
16. inability or unwillingness to comply with protocol-specified procedures which, in the opinion of the Investigator, would make the subject unsuitable for study participation.

